11.4. Recording Adverse Events

AEs spontaneously reported by the patient and/or in response to an open question from the study personnel or revealed by observation will be recorded during the study at the investigational site.

Information about AEs (and SAEs) will be collected from the time the patient signs the informed consent for this study and takes the first study dose of XADAGO until the patient’s last follow-up visit. The AE term should be reported in standard medical terminology when possible. For each AE, the investigator will evaluate and report the onset date, resolution date, intensity, causality, action taken, serious outcome (if applicable), and whether or not it caused the patient to discontinue the study.

Intensity will be assessed according to the following scale:

- Mild (awareness of sign or symptom, but easily tolerated)
- Moderate (discomfort sufficient to cause interference with normal activities)
- Severe (incapacitating, with inability to perform normal activities)

It is important to distinguish between serious and severe AEs. Severity is a measure of intensity whereas seriousness is defined by the criteria under Section 11.2.2. An AE of severe intensity may not be considered serious.

11.4.1. Non-Serious Adverse Event (AE)

If a non-serious AE occurs for any patient after signing an informed consent for this study and having taken XADAGO, the site should record the AE in the patient's source medical record and eCRF in as real time as possible, but no later than 5 business days of observation or notification that such an event has occurred. The patient's medical record and eCRF should be completed with as much information as is available at that time and the Sponsor will contact the site if additional information is required regarding the non-serious AE. Additional instruction for entering non-serious AE data in the eCRF is provided in the investigator site file (study binder).

11.4.2. Serious Adverse Event (SAE)

All SAEs (related and unrelated) that occur for any patient after signing an informed consent for this study and having taken XADAGO must be recorded by the investigator and reported. The site should record the SAE in the patient's source medical record within 24 hours of observation or notification that such an event has occurred. The patient's medical record should be completed with as much information as is available at that time with the knowledge that full clinical details may not be immediately available. The Sponsor will contact the site if additional information is required regarding the SAE. In addition, an SAE form located in the ISF binder must be completed and submitted to (see [Table 1](#) for details).

All SAEs must be followed until they resolve or stabilize (i.e., a new baseline has been established). The PI must provide the Sponsor with all relevant follow-up information necessary to facilitate a thorough understanding of the experience and judgment regarding the relationship to XADAGO. Patients who discontinue because of an SAE before study completion will be contacted 7 days (± 3 days) after discontinuation to determine if the SAE has resolved, continues unabated, or has reached a new baseline.

Reports of congenital abnormalities/birth defects are SAEs. Spontaneous miscarriages should also be reported and handled as SAEs. Elective abortions without complications should not be handled as AEs.

11.4.3. Pregnancy and Lactation

Pregnancy is not considered an AE. According to the XADAGO Package Insert, XADAGO is classified as Pregnancy Category C. There are no adequate and well-controlled studies of XADAGO in pregnant women. XADAGO should be used during pregnancy only if the potential benefit justifies the potential risk to the fetus.

It is not known whether this drug is present in human milk. Because many drugs are excreted in human milk and because of the potential for serious adverse reactions in nursing infants from safinamide, a decision should be made whether to discontinue nursing or to discontinue drug, taking into account the importance of the drug to the mother.

12. STATISTICAL METHODS

12.1. General Statistical Considerations

All assessments will be summarized at specified time points. Continuous variables will be summarized using the number of patients, mean, standard deviation (SD), and minimum, median, and maximum values. Categorical variables will be summarized using the number and percentage. All data will be summarized according to cohort and overall.

Endpoints are defined at Study Day 60 (primary endpoint). Descriptive statistics will be provided for all data collected. All tests of significance, unless otherwise stated, will be performed using a two-sided alpha at 0.05.

All analyses will be performed using SAS[®] Version 9.3 or higher (SAS Institute, Inc., Cary, North Carolina, USA).

12.2. Analysis Populations

The 2 analysis populations are defined in the study's Statistical Analysis Plan (SAP) as follows:

- Safety Population: All patients who sign informed consent for the study, complete baseline assessments, and receive at least 1 dose of XADAGO.
- Evaluable Population: All patients in the safety population who complete at least the MDS-UPDRS assessment at the Study Day 60 visit.

The principal analysis of the primary endpoint will be conducted for the evaluable population. Sensitivity analysis of the primary endpoint will be carried out for the safety population. Safety summaries will be provided for the safety population.

Eligible, consented, and enrolled study participants will be analyzed based on concomitant PD medication regimen change at Baseline:

Cohort A – Patients that have switched to XADAGO from a Dopamine Agonist

Cohort B – Patients that have switched to XADAGO from an MAO-B inhibitor

Cohort C – Patients that are MAO-B inhibitor naïve

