8.1.1. Screening / Baseline Assessments (Visit 1, Study Day 1)

The Screening Visit and the Baseline Assessment Visit may occur on the same day. During the Screening Visit, patients who provide written consent to participate in the study and HIPAA authorization to use their personal health information will be screened for inclusion in the study according to the following procedures:

- Assessment of eligibility criteria (i.e., Inclusion [[Section 9.1](#)] and Exclusion [[Section 9.2](#)] Criteria)
- Collection of demographics and medical history information, including history of PD and other neurological conditions

For patients determined to be eligible for the study, Baseline Assessments should be conducted at the same visit that Screening occurs. If the patient requires a separate Baseline Assessment Visit, it should occur no more than 7 days after the Screening Visit.

Patients will arrive at the Investigator’s clinic in an “on” motor state. The following activities and outcome assessments (Baseline Assessments) will be completed at the clinic Baseline Visit:

- Presentation of study instructions relative to XADAGO administration, concomitant medications, reporting of safety events, patient and Care Partner (if applicable), completion of CROs and PROs, downloading and training on the eCOA system, and documentation of other study data
- Registration and training on the eCOA system (in which the patient will report PRO results)
- Assessment of concomitant medications
- MDS-UPDRS by the PI/certified HCP designee

- PDQ-39 by the patient
- MoCA by the PI/certified HCP designee
- Study Day 1 administration of XADAGO

8.1.2. Telephone Follow-up with Patient by Study Site Staff (Visit 2, Study Day 30)

All patients will be contacted by telephone on Study Day 30. If the patient is scheduled for a routine clinic visit within ± 5 days of the Study Day 30 visit, the study assessments may be performed in person with the patient during the routine clinic visit.

The following assessments will be completed:

- Review of patient information relevant to XADAGO administration and concomitant medication administration
 - Daily record (e.g., electronic diary or log) will be available for the patient to enter information relevant to XADAGO and concomitant medications taken if patient decides to utilize
- PRO assessment:
 - TSQM-9

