12.9. Analysis

12.9.1. Primary Outcome Analysis (Observational Assessments)

The change in MDS-UPDRS, PDQ-39, and MoCA from the Baseline Assessment Visit to the Primary Endpoint (Study Day 60) will be analyzed and described in detail in the SAP.

For the endpoints of CGI-C and PGI-C, the data will be dichotomized to have two categories, with 'very much improved' and 'much improved' into one category and the remaining levels into the other.

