### **6.5.3. ITT Population**

The ITT Population is defined as all subjects who sign informed consent for the study, complete baseline assessments, and receive at least 1 dose of XADAGO. ITT population will be used to analyze all efficacy endpoints except MDS-UPDRS.

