#### **6.5.4. Evaluable Population**

The Evaluable population comprises all subjects in the safety population who complete at least the MDS-UPDRS assessment at the Study Day 60 visit. Evaluable population will be used to analyze MDS-UPDRS endpoint.

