##### **6.7.3. Change from Baseline**

Change from baseline is calculated as (post-baseline result – baseline result).

Percent change from baseline is calculated as (change from baseline/baseline result \* 100).

If either the baseline or the post-baseline result is missing, the change from baseline and/or percentage change from baseline is set to missing as well.

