## **6.8. Handling of Missing Data**

### **6.8.1. Missing Efficacy Endpoints**

The missing efficacy data will be imputed by Last-Observation-Carried-Forward (LOCF) method.

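### The SAP analyses MDS-UPDRS only in patients with a Day 60 MDS-UPDRS and moves PDQ-39 and MoCA to the ITT set, contrary to Protocol 12.2, and MDS-UPDRS loses its promised safety-population check

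*Protocol*

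**What the plan says.** **Protocol.** Section 12.2 makes no distinction between scales: "The principal analysis of the primary endpoint will be conducted for the evaluable population". It then adds a check: "Sensitivity analysis of the primary endpoint will be carried out for the safety population". Section 12.9.1 shows which scales are meant: "The change in MDS-UPDRS, PDQ-39, and MoCA from the Baseline Assessment Visit to the Primary Endpoint (Study Day 60) will be analyzed".

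**SAP populations.** Section 6.5.3 introduces an ITT set whose definition matches the Safety Population of 6.5.2 (consent, baseline assessments, at least one dose). It assigns the scales as follows: "ITT population will be used to analyze all efficacy endpoints except MDS-UPDRS". Section 6.5.4 completes the split: "Evaluable population will be used to analyze MDS-UPDRS endpoint". Membership of the evaluable set requires an MDS-UPDRS at Day 60.

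**SAP analysis.** Section 8.4 gives a summary by cohort and overall, and a paired t-test for the continuous endpoints. No section of the SAP text describes a sensitivity analysis.

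**SAP missing data.** Section 6.8.1 says: "The missing efficacy data will be imputed by Last-Observation-Carried-Forward (LOCF) method". Section 6.7.3 says that when the baseline or post-baseline result is missing, "the change from baseline and/or percentage change from baseline is set to missing as well". The SAP does not say which rule takes precedence, or whether LOCF may carry a baseline value forward.

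**The concern.** The study has no control group, so the result is the mean change from Baseline. If patients who do badly are less likely to reach Day 60, a mean restricted to those assessed at Day 60 looks better than the mean for everyone who started. The protocol foresaw this by pairing the evaluable-set analysis with one in the safety population. A programmer who follows the SAP will not produce the second analysis for MDS-UPDRS, and will not produce the protocol's principal analysis for PDQ-39 and MoCA.

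The split may also mean that one dropout is treated in two ways across scales which the protocol groups together: left out for MDS-UPDRS, but kept in for PDQ-39 and MoCA with a carried-forward value. Results reported side by side would then rest on different patients and different assumptions. The SAP gives no reason for this. Two-sided 5% tests are planned (SAP 6.4), and Protocol 12.6 foresees publication of interim results, so the figures are likely to be read as estimates of change on treatment.

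**Working it through.** **1. Is there a figure in the plan to reproduce?** No. The documents state no dropout rate, effect size, SD or power. Up to 600 screened giving up to 540 eligible and evaluable implies 1 - 540/600 = 10% loss, but that mixes ineligibility with loss to follow-up and is not a dropout assumption.

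**2. Which analyses survive in the SAP?**

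| Scale | Protocol principal | Protocol sensitivity | SAP |
|---|---|---|---|
| MDS-UPDRS | Evaluable | Safety | Evaluable only |
| PDQ-39, MoCA | Evaluable | Safety | ITT only (same definition as Safety) |

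MDS-UPDRS loses the right-hand protocol column. PDQ-39 and MoCA lose the left-hand one.

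**3. What can LOCF carry forward?** Between Baseline and Day 60 there is one contact: "All patients will be contacted by telephone on Study Day 30" (Protocol 8.1.2). TSQM-9 is the only scale collected then. PDQ-39, MoCA and MDS-UPDRS have no value between Baseline and Day 60.

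- If SAP 6.8.1 governs and Baseline may be carried forward, a patient lost before Day 60 has a change of 0 on PDQ-39 and MoCA and is absent from MDS-UPDRS.
- If SAP 6.7.3 governs, the change is missing. PDQ-39 and MoCA become observed-case analyses and the gap largely disappears.

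**4. Size of the gap under the first reading.** For dropout share d:

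ITT mean = (1 - d) × completer mean + d × 0 = (1 - d) × completer mean.

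At d = 5%, 10%, 20% and 30% (assumed), the ITT mean is 0.95, 0.90, 0.80 and 0.70 of the completer mean.

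**5. Size of the bias in a completers-only mean.** Assume completers change by -4 points and leavers by k. The all-patient mean is (1 - d)(-4) + d·k, and the overstatement is 4 divided by its absolute value, minus 1.

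| d | k | All-patient mean | Overstatement |
|---|---|---|---|
| 5% | +2 | 0.95(-4) + 0.05(2) = -3.7 | 4/3.7 - 1 = 8% |
| 15% | +2 | 0.85(-4) + 0.15(2) = -3.1 | 4/3.1 - 1 = 29% |
| 20% | +2 | 0.80(-4) + 0.20(2) = -2.8 | 4/2.8 - 1 = 43% |
| 15% | 0 | 0.85(-4) = -3.4 | 4/3.4 - 1 = 18% |
| 15% | -4 | -4.0 | 0% |

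**6. Would a safety-population run with LOCF be enough?** Take N = 540 and completers with mean change/SD = 0.3 (assumed). At 10% loss there are 486 completers, and t = 0.3 × √486 = 6.61. Adding 54 zeros gives a mean of 0.27 SD and a variance of (485 + 486 × 0.09 - 540 × 0.0729)/539 = 0.908, so t = 0.27 × √540/√0.908 = 6.58. The 95% interval half-width falls to about 0.90 of the completer width. At 30% loss, t goes from 5.83 to 5.76 and the half-width to about 0.71. Carrying Baseline forward shrinks the mean, hardly moves the test and makes the interval look more precise. It is a weak check.

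**The case against.** Four points on the other side deserve weight.

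- **The SAP does not clearly set leavers to zero change.** A reader might infer that LOCF does this for PDQ-39 and MoCA. That needs 6.8.1 to override 6.7.3 and Baseline to count as an observation to carry. The SAP settles neither, so the two-way handling is conditional.
- **The safety-population analysis is not lost for every scale.** A reader might infer that all three scales lose it. PDQ-39 and MoCA are still analysed in a set defined like the Safety Population; only MDS-UPDRS has no all-patient run. The omission is also by silence: the protocol sentence still stands, so this is a conflict, not a withdrawal.
- **MDS-UPDRS is not ranked first.** A reader might take it as the main scale because the evaluable set is built on it. Protocol 12.9.1 lists the three scales together without an order.
- **Loss may be small and the stakes modest.** Patients who stop XADAGO may stay and be assessed (Protocol 10.1.4), so those at issue are study dropouts, not treatment stoppers. The study is observational, with no decision rule and no planned comparison between scales.

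The first three points limit the claim, and it is stated here within those limits. The fourth reduces the likely size but does not remove the issue. Patients can still withdraw or be lost to follow-up (Protocol 9.4), and SAP 7.2 allows further exclusions from the evaluable set for protocol violations.

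**Conclusion.** The point holds as a conflict between the two documents with a practical consequence. Under the SAP as written, the MDS-UPDRS result is conditional on a Day 60 assessment and nothing tests that condition, while PDQ-39 and MoCA are not analysed in the set that the protocol calls principal. Neither conclusion depends on a numerical assumption.

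The size does depend on assumptions. With completers at -4 and leavers at +2, the overstatement runs from about 8% to 43% over 5% to 20% loss. At 15% loss it runs from 0% to 29% as leavers go from changing like completers to worsening by 2. No single figure in that range can be called the expected bias, because the documents give no dropout rate, effect size or outcome for leavers. The shrinkage of the PDQ-39 and MoCA means by the dropout share applies only if LOCF governs and may carry Baseline forward.

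This should be corrected before database lock, but it does not undermine the study.

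**What to change.** 1. In SAP 6.5 and 8.4, name the protocol's evaluable set as the principal set for PDQ-39, MoCA and MDS-UPDRS.
2. Restore the safety-population sensitivity analysis for all three scales, MDS-UPDRS included. It will also bring back any Day 60 PDQ-39 or MoCA value from a patient without a Day 60 MDS-UPDRS. For patients with no Day 60 value on a scale, assign a prespecified range of changes (same as completers, no change, worsening) instead of relying on LOCF alone. Judge the check on how far the mean moves; intervals from single filled-in values are too narrow.
3. In SAP 6.7.3 and 6.8.1, state which missing-data rule governs the principal analysis and whether Baseline may be carried forward.

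A repeated-measures model is not a remedy for patients who leave before Day 60. They have only Baseline on these scales, and the extension visits are open only to those who complete the Main Study.

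Cost: SAP wording and one extra set of tables. No new data collection is needed.

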12.3. Sample Size and Decision Rules

This is an observational study that will not assign treatment to patients. Patients will be analyzed collectively and in one of 3 cohorts based on the study entry criteria. A sample size of up to 540 patients was selected to ensure a meaningful representation in each of the 3 cohorts.

12.4. Handling of Missing Values

PROs will handle missing values per the recommended process for that instrument. In general, missing item values for PRO instruments will not be imputed. Missing values will usually result in non-computational item scores for the patient.

Missing visit information will usually be handled by analyzing using last-observation-carried-forward (LOCF) imputations.

12.5. Subgroups and Covariate Adjustment

Age, sex, and disease duration will be included in any subgrouping and/or covariate modeling. When variables are used in modeling, the inclusion in model will only stay if the p-value < 0.10 for those situations.

12.6. Interim Analysis

Interim data analyses will be performed periodically to provide study updates and to support potential presentation of interim results via posters, publications, and other data dissemination vehicles. Since this study is observational only and treatments are not assigned to specific patient/treatment groups, these interim analyses will have no statistical implications.

12.7. Population and Patient Disposition

Frequency of patients enrolled, safety population, and evaluable patients will be displayed. Populations will be reported by cohort, site.

Patient disposition will be summarized in each cohort along with reason of discontinuation. Frequency and percentages of patients completing and discontinuing the study prior to the primary endpoint (Study Day 60) and prior to the last study visit (Study Day 180) will be analyzed.

12.8. Demographic and Baseline Characteristics

Demographic and baseline characteristics will include age, sex, weight, height, body mass index (BMI), race, and vital signs. Baseline characteristics will be detailed for all PROs and will be analyzed descriptively.

12.9. Analysis

12.9.1. Primary Outcome Analysis (Observational Assessments)

The change in MDS-UPDRS, PDQ-39, and MoCA from the Baseline Assessment Visit to the Primary Endpoint (Study Day 60) will be analyzed and described in detail in the SAP.

For the endpoints of CGI-C and PGI-C, the data will be dichotomized to have two categories, with 'very much improved' and 'much improved' into one category and the remaining levels into the other.

12.9.2. Safety Analysis

Serious and non-serious AEs will be collected as part of this study and reported for each cohort and overall.

13. STUDY MONITORING AND QUALITY CONTROL

13.1. Study Monitoring

The Sponsor is responsible for monitoring the progress of this study and overseeing data quality.

13.2. Inspection of Records

The Sponsor, designated representatives, the IRB, and any applicable regulatory agency will be provided with direct access to all information in original source documents and/or certified copies of original records of clinical findings, observations, or other activities in the clinical study necessary for the reconstruction and evaluation of the study.

13.3. Site Audits

It may be necessary for the Sponsor, designated representatives, and/or a regulatory agency to audit an investigative site. The purpose of an audit is to assess the accuracy, adequacy, and consistency of the study records and patient data, as well as to assess the site's adherence to the procedures described in the study protocol. Direct access must be provided to all information in original source documents (if applicable) and/or certified copies of original records of clinical findings, observations, or other activities in the clinical study necessary for the reconstruction and evaluation of the study.

13.4. Quality Control

14. ETHICS

This study will be conducted according to US CFRs dealing with Protection of Human Subjects (US 21 CFR Part 50) and IRBs (US 21 CFR Part 56); the Nuremberg Code; and the Declaration of Helsinki, revised version of Fortaleza, Brazil, October 2013 (in compliance with FDA guidance).

14.1. Ethics Review

The US FDA regulates studies of drugs, biologics, and medical devices. Consequently, these studies are subject to regulations and guidance issued by the FDA and are included in the following parts of the US CFR and guideline document:

- 21 CFR Part 50 - Protection of Human Subjects
- 21 CFR Part 56 - Institutional Review Boards
- 21 CFR Part 314.80 - Post-marketing reporting of adverse drug experiences

Copies of these materials can be downloaded from the FDA's website at www.fda.gov.

The purpose of these regulations, legal obligations, and guidelines is to define the standards and principles for the proper conduct of clinical trials that have been developed by the medical, scientific, and regulatory communities. They are not intended to impede or restrict clinical research.

14.2. Ethical Conduct of the Study and Institutional Review Board (IRB) Approval

The Sponsor of this study is responsible for selecting qualified investigators, providing investigators with the information needed to properly conduct a study, properly monitoring the study, and ensuring that the FDA and all participating investigators are properly informed of significant new information regarding post-marketing adverse drug experiences or risks associated with the marketed drug XADAGO.

Before the study can be initiated, the PI must obtain written IRB approval from the IRB of the PI's institution and/or a central IRB (whichever is applicable) that complies with the requirements relating to IRBs. The final study protocol and final version of the Informed Consent Form (ICF) must be approved or given a favorable opinion in writing by an IRB as appropriate. The PI must submit written approval to the Sponsor (or designee) before he/she can enroll any patient into the study.

If an amendment(s) to the study protocol becomes necessary, the Sponsor will provide the protocol amendment(s) and the PI will submit the written amendment(s) to his or her IRB for approval before amendment implementation. In addition, the PI's IRB must approve all site-specific advertising used to recruit patients for the study. Re-approval by the IRB must be obtained annually, if the study is more than 1 year in duration.

Progress reports will be submitted to the IRB annually or at a frequency requested by the IRB.

The PI is also responsible for providing the IRB with reports of all unanticipated problems involving risk to human patients or others, including serious and non-serious AEs.

